## **B5.4 Data Collection**

### **Blood Sampling and Total Blood Volume Collected**

Serial blood draws collected during the stable isotope infusion studies (see **Figure 6**) will be analyzed for isotopic enrichments, blood urea nitrogen, insulin, and AA concentrations. There are 16 blood draws per infusion study. 9.5mL of blood will be drawn at each of the 16 draws, for a total of 152 mL per infusion study and 304 mL over the course of the study. Sufficient blood will be drawn and archived to allow for additional analyses of related metabolic biomarkers sensitive to EAA, resistance exercise, and energy deficit.

### **Stable Isotope Analysis and Calculations of Whole-body and Muscle Protein Kinetics**

*All stable isotope analyses on de-identified, coded blood and muscle samples will be conducted by [name] at UAMS (data sharing agreement attached is provided with this protocol). No samples will be stored at UAMS for future analyses because the entire sample provided will be processed for the assays below.*

#### **Blood Sample Processing for Isotopic Enrichment**

Blood samples will be precipitated with 125  $\mu$ L of 10% sulfosalicylic acid (SSA) and centrifuged. The internal standard technique will be used to determine blood EAA concentrations. Free amino acids (AA) will be extracted from 300  $\mu$ L supernatant fluid by cation exchange chromatography and dried under Speed Vac (Savant Instruments, Farmingdale, NY or similar model). Enrichments of phenylalanine and tyrosine will be measured on the tert-butyldimethylsilyl derivative with the use of gas chromatography-mass spectrometry (models 7890A/5975; Agilent Technologies, Santa Clara, CA or similar model) [46, 47]. Ions of mass-to-charge ratio of 234, 235, and 239 for phenylalanine, of 302 and 308 for leucine, and of 466, 467, 468, and 470 for tyrosine will be monitored with electron impact ionization and selective ion monitoring.

#### **Muscle Sample Processing for Isotopic Enrichment**

Muscle biopsy tissue samples taken from the vastus lateralis muscle will be cleaned of visible fat, blotted of excess blood, then frozen in liquid nitrogen, and stored in a  $-80^{\circ}\text{C}$  freezer until later analysis. Upon thawing, muscle tissues will be weighed, and tissue proteins precipitated with 0.5 mL of 4% SSA. The tissues will then be homogenized and centrifuged for collection of supernatant. The procedure will be repeated two more times, and tissue intracellular free AAs extracted from the pooled supernatant via the same cation exchange chromatography stated in plasma analyses and then dried under the Speed Vac. The remaining muscle pellet will be washed, dried, and hydrolyzed in 0.5 mL of 6 N HCl at  $105^{\circ}\text{C}$  for 24-h. Enrichments from muscle free and bound tracers will be determined as in plasma analyses.

#### **Whole-body Protein Turnover and Muscle Fractional Synthesis Calculations**

Calculations of whole-body protein synthesis (PS) and protein breakdown (PB) rates will be performed based on the determinations of the rate of appearance (Ra) into the plasma of phenylalanine and tyrosine and the fractional Ra of endogenous tyrosine converted from phenylalanine [48]. Plasma enrichments of phenylalanine and tyrosine tracers will be curve-fitted with a cubic spline method using Graphpad Prism 5 (Graphpad Software, La Jolla, CA or equivalent). Whole body protein turnover will be calculated by dividing kinetic values of a single essential amino acid (i.e., phenylalanine), which cannot be synthesized in the body, by its fractional contribution to protein. For the calculations for whole-body PB rate, contribution from exogenous EAA and tracers infused will be subtracted from total Ra. Appropriate skew correction will be made for  $^{13}\text{C}$ -labeled tracers [48].

Calculation of resting and post-exercise muscle FSR will be determined as the incorporation of the phenylalanine tracer from biopsy one (180 min) to biopsy two (420 min) using the precursor-product model [49].

The following equations will be used for calculations of whole-body and muscle protein kinetics:

$$\text{Total plasma } R_a = F/E$$

$$\text{Fractional } R_a \text{ of Tyr from Phe} = E_{\text{Tyr M+4}}/E_{\text{Phe M+5}}$$

$$\text{Phe hydroxylation} = \text{fractional } R_a \text{ of Tyr from Phe} \times R_{a|\text{Tyr}}$$

$$PS = [(R_{a|Phe} - \text{Phe hydroxylation}) \times 25]$$

$$PB = [(R_{a|Phe} - F_{Phe}) \times 25 - PRO_{MEAL}]$$

$$NB = PS - PB$$

$$FSR (\%) = [(E_{p2} - E_{p1}) / (E_m \times t)] \times 60 \times 100$$

where enrichment (E) is expressed as tracer-to-tracee ratio (TTR) for calculation of PB or mole percent excess for calculation of muscle FSR, calculated as  $TTR / (TTR + 1)$ . E is enrichment of respective tracers at plateau. F is respective tracer infusion rate into a venous side:  $F_{Phe}$  for phenylalanine tracer.  $E_{Tyr\ M+4}$  and  $E_{Phe\ M+5}$  are plasma enrichments of tyrosine tracers at M+4 and M+5 relative to M+0, respectively. Correction factor of 25 is for conversion of value for phenylalanine to protein based on the assumption that contribution of phenylalanine to protein is 4% ( $100/4 = 25$ ) [50].  $PRO_{MEAL}$  is the amount of exogenous EAA (g) that appeared in the circulation, which was calculated as total amount of EAA provided (if any), based on the assumption that 85% of the EAA ingested was absorbed [51]. Phenylalanine hydroxylation is the  $R_a$  of tyrosine derived from phenylalanine through hydroxylation.  $E_{P1}$  and  $E_{P2}$  are the enrichments of bound L-[ring- $^2H_5$ ]-phenylalanine in the 180 min and 420 min biopsies, respectively.  $E_m$  is the calculated mean value of the enrichments of [ring- $^2H_5$ ]-phenylalanine in the intracellular or plasma pool.  $t$  is the time in minutes elapsed between muscle biopsies. Factors 60 and 100 were used to express muscle FSR in percent per hour.

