**Figure 6. Infusion Protocol**

enriched with L-[ring-H5]-phenylalanine to 4% to limit potential disturbances in isotopic steady-state. Volunteers will remain rested during serial blood sampling over a 3-h period following ingestion. Final biopsies will be taken from each leg at the end of the 3-h period. There will be a total of 2 incisions per EAA trial, one on the rested leg and one on the exercised leg. A total of 5 muscle biopsies will be collected from each volunteer per EAA trial; 2 through 1 incision on the exercised leg and 3 through 1 incision on the rested leg (2 new incisions will be made on the subsequent EAA trial. The incisions on EAA trial 1 will NOT be used for trial 2). Blood samples will be collected at regular intervals to assess isotopic enrichments for kinetic calculations, insulin, blood urea nitrogen, and amino acid concentrations (**Figure 6**).

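### After the drink, whole-body kinetics are defined from a plateau that cannot be assumed, and an amount is subtracted from a rate with no common interval; the unstated reading time drives the net-balance contrast

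*Combined protocol and SAP*

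**What the plan says.** The equations are in B5.4, under Whole-body Protein Turnover and Muscle Fractional Synthesis Calculations. In plain notation:

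- Ra = F/E, where F is the tracer infusion rate. The definitions below the equations add: "E is enrichment of respective tracers at plateau".
- Hydroxylation = (tyrosine M+4 enrichment / phenylalanine M+5 enrichment) × Ra of tyrosine.
- PS = (Ra_Phe − hydroxylation) × 25.
- PB = (Ra_Phe − F_Phe) × 25 − PRO_MEAL.
- NB = PS − PB.

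PRO_MEAL is an amount in grams: the EAA given, "based on the assumption that 85% of the EAA ingested was absorbed". The same section also says: "Plasma enrichments of phenylalanine and tyrosine tracers will be curve-fitted with a cubic spline method". It does not say which times are read from the fitted curve, whether the curve is integrated, or over what interval.

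B5.3 has the drink taken in 5-10 min, with its phenylalanine enriched to 4% to limit disturbance of the isotopic steady state. It continues: "Volunteers will remain rested during serial blood sampling over a 3-h period following ingestion". B5.1 names whole-body protein balance as a primary outcome alongside muscle protein synthesis, and Hypotheses 2 and 3 in B4 rest on it.

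**The concern.** A plateau reading suits the fasted tracer infusion. It does not suit a bolus, during which unlabelled and labelled phenylalanine enter together and at a changing rate. Two instructions then stand side by side, a plateau value and a spline-fitted curve, and the plan does not say which supplies Ra and hydroxylation after the drink.

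The breakdown equation adds a second problem. Its first term is a rate and its second is a total, so PB and NB have no defined units after the drink until an interval is stated.

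At stake is the dose comparison in a primary outcome. If the reading time can move that contrast, it has to be fixed before the analysis.

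**Working it through.** **Plan's own figure.** The plan gives no expected difference in net balance. B5.8.1 claims more than 95% power for it but states neither a difference nor an SD, so this cannot be reproduced. The muscle FSR sample size is a separate matter and is not affected.

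**Inputs from the documents.** Doses 0.10 and 0.30 g/kg (difference 0.20); phenylalanine 0.63 g per 10 g of mixture (6.3%); absorbed share 0.85; protein factor 25; follow-up 180 min.

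**Step 1: what net balance measures.**

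NB = 25 × (Ra_Phe − hydroxylation) − [25 × (Ra_Phe − F_Phe) − PRO_MEAL] = PRO_MEAL + 25 × (F_Phe − hydroxylation)

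Ra_Phe cancels. PRO_MEAL is set by dose and F_Phe by the pump, so hydroxylation is the only measured response left. Hydroxylation itself uses Ra of tyrosine, which is F/E, so the plateau definition enters NB there.

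**Step 2: dose contrast, with the same infusion rate in both trials.**

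Contrast = 0.85 × 0.20 − 25 × (difference in hydroxylation) = 0.170 g/kg − 25 × (difference in hydroxylation)

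If hydroxylation is read after it has returned to baseline in both trials, the last term is zero. The contrast is then 0.170 g/kg by construction, or 13.6 g at an assumed 80 kg.

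**Step 3: rate against amount.** Spread over the 3-h window, the PRO_MEAL contrast is 0.170/3 = 0.057 g/kg per hour. Set against an hourly rate without division, it counts as 0.170. The plan does not say which is meant.

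**Step 4: scale.** The Ra term carries absorbed drink phenylalanine × 25 = 0.063 × 0.85 × 25 = 1.34 g per g of drink. PRO_MEAL removes 0.85 g per g, and 0.85/1.34 = 63%. Between doses, 0.20 × 0.063 × 0.85 × 25 = 0.268 g/kg against 0.170 g/kg.

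The listed amino acids sum to 9.14 g per 10 g (8.33 g without arginine), so the phenylalanine share could be 6.3-7.6%. A higher share widens the gap.

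**Step 5: both defects together.** Let f be the share of the extra absorbed phenylalanine hydroxylated within 3 h. The range is assumed; the documents give none. Contrasts are in g/kg:

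| f | Time and scale consistent: 0.268 × (1 − f) | Read after return to baseline, PRO_MEAL as written | Time corrected only: 0.170 − 0.268 × f | Scale corrected only, read after return to baseline |
|---|---|---|---|---|
| 10% | 0.241 | 0.170 | 0.143 | 0.268 |
| 20% | 0.214 | 0.170 | 0.116 | 0.268 |
| 30% | 0.187 | 0.170 | 0.090 | 0.268 |

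Correcting only one of the two does not reach the consistent figure.

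**Step 6: does the reading time matter in practice?** A two-pool phenylalanine/tyrosine simulation for an 80 kg volunteer included the 4% enrichment of the drink. Its kinetic inputs are assumptions: basal phenylalanine Ra 45 µmol/kg/h; phenylalanine tracer 3-4 and tyrosine tracer 2 µmol/kg/h; endogenous tyrosine Ra 35 µmol/kg/h; 12-20% of flux hydroxylated at baseline; absorption half-life 15-60 min; phenylalanine pool half-life 20-40 min; tyrosine pool half-life 30 min.

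- In the base run, plasma phenylalanine enrichment falls from 0.089 to 0.060 (high dose) and 0.073 (low dose), then returns to 0.085-0.088 by 180 min.
- Across runs, with PRO_MEAL as written, the high-minus-low NB is 7.0-11.7 g when integrated over 0-180 min and 10.8-13.0 g when read at 150-180 min.
- Against the integrated value from the same run, the late reading is 0.6-3.8 g higher and a 30-60 min reading is 0.4-3.4 g lower.
- With integrated hydroxylation and the drink term on the phenylalanine × 25 basis, the difference is 13.9-19.2 g, above the late-reading figure in every run.

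**The case against.** The best defence is that the plan already intends a time-course calculation. It collects serial samples, fits a spline to the plasma curves, and enriches the drink's phenylalanine to limit the disturbance. The two enrichments in the hydroxylation ratio are defined simply as plasma enrichments, without reference to a plateau. On this reading, one steady-state sentence has been carried over from the fasted calculation. Figure 6, which holds the sampling scheme, is not shown in the text available, and the methods sources cited for the calculations cannot be consulted here.

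Much of this stands: it would be wrong to call the plan plateau-only. It does not remove the point. The plateau sentence is the stated definition of E, Ra = F/E is the stated formula, and nothing says what is taken from the spline. The drink's enrichment is meant only to limit the disturbance, and under the assumed kinetics a dose-dependent dip remains. The mismatch between rate and amount does not depend on any kinetic assumption.

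A reader might go further and infer that a late plateau reading inflates the high-dose net balance. Comparing 0.170 with 0.143, 0.116 and 0.090 g/kg would make it 19%, 46% or 90% too large and Hypothesis 2 favoured. The documents do not support this:

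- They nowhere specify a late reading, and an early one moves the contrast the other way.
- They do not show that hydroxylation returns to baseline within 3 h.
- They subtract 85% of the EAA grams, not the whole drink.
- The benchmark in that comparison itself under-credits the drink. On the plan's own × 25 scale, 0.170 g/kg lies below the consistent values of 0.241, 0.214 and 0.187. It would exceed them only if f were above about 37% (1 − 0.170/0.268).

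**Conclusion.** The point holds as an undefined and internally inconsistent calculation of a primary outcome. After the drink, the plateau definition and the spline are not reconciled, and PB and NB combine a rate with an amount over no stated interval. The reading time can fix the dose contrast at 0.170 g/kg regardless of response, or shift it by grams in either direction. The cancellation of Ra_Phe, the 0.170 g/kg and the mismatch of units follow from the plan's equations. The 0.268 g/kg also takes phenylalanine as 6.3% of the dose. The values by f and the simulated ranges rest on the stated assumptions.

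No net direction of bias is established, and no claim that either hypothesis is favoured should be drawn from this. The definition should be settled before the primary outcomes are analysed and the code is broken.

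**What to change.** In B5.4:

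1. Keep the plateau definition of E for the fasted pre-exercise period only.
2. For the post-drink period, define Ra, hydroxylation, PS, PB and NB from the spline-fitted curves, integrated from drink to final sample (0-180 min). Use the same window in both trials and report per kg per 180 min.
3. Express the exogenous term over that same interval and on the same basis as the kinetic terms: absorbed drink phenylalanine × 25. That is about 1.34 g per g of drink at 6.3% phenylalanine and 85% absorption, in place of 0.85 g per g. Confirm the phenylalanine share from the product composition, since the listed amounts do not sum to 10 g.

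Items 2 and 3 must be made together. Integrating hydroxylation alone moves the contrast to 0.143, 0.116 or 0.090 g/kg, further from the consistent values.

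The cost is wording in B5.4 and a little analysis work. The serial samples and the spline fit are already planned, and no volunteer procedure changes.

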##### **Hypotheses**

1. Resting and post-resistance exercise muscle protein synthesis will be stimulated to a greater degree with higher (0.30 g/kg) versus lower (0.10 g/kg) EAA intake during acute, moderate energy deficit.
2. Resting and post-resistance exercise whole-body protein balance will be greater with higher (0.30 g/kg) versus lower (0.10 g/kg) EAA intake during acute, moderate energy deficit.
3. Resting and post-resistance exercise whole-body protein balance will be more positive with higher (0.30 g/kg) versus lower (0.10 g/kg) EAA intake during acute, moderate energy deficit due to a greater increase in whole-body protein synthesis.
4. Resting and post-resistance exercise skeletal muscle anabolic signaling will be stimulated to a greater degree with higher (0.30 g/kg) versus lower (0.10 g/kg) EAA intake during acute, moderate energy deficit.

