At 120-min, a muscle biopsy of the vastus lateralis will be taken on the non-exercised leg only to assess basal (fasting/resting) muscle protein kinetics. After the muscle biopsy, volunteers will remain rested until they perform a heavy-load, high volume, single leg-resistance exercise bout at 195-min that consists of 8 sets X 10 repetitions on the leg-press and leg-extension machines [9]. Both exercises will be performed at 80% of a pre-determined one repetition maximum (1RM) with a 2-min rest interval between sets. Volunteers will have ~45-min to complete the exercise bout. In the event the volunteer is unable to complete the prescribed workload; the workload will be reduced by 4.5 kg as previously described [9]. This will be repeated until the participant can complete the prescribed work. Approximately 5-min after completing the exercise bout (240-min), a muscle biopsy will be taken from the vastus lateralis of the exercised and non-exercised (rested) legs (the exercised and non-exercised leg will be the same between trials). Immediately after the biopsies, volunteers will consume the appropriate dose (i.e., an artificially flavored beverage) of free-form EAA in 5-10-min [Reginator™; EAA content per 10 g of the mixture: 0.15 g histidine, 3.66 g leucine, 0.94 g isoleucine, 1.65 g lysine, 0.3 g methionine, 0.63 g phenylalanine, 0.89 g threonine, 0.1 g valine, 0.006 g tryptophan, and 0.81 g arginine (conditionally essential under stress)]. The phenylalanine content of the beverage will be artificially

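### After the drink, the phenylalanine Ra formula counts only intravenous tracer although the drink carries the same tracer at 4%, so the split of net balance into whole-body synthesis and breakdown is biased, more so at the higher dose

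*Combined protocol and SAP*

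**What the plan says.** Section B5.4 (Whole-body Protein Turnover and Muscle Fractional Synthesis Calculations) gives one set of equations for all periods:

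- Total plasma Ra = F/E. The terms are defined as "E is enrichment of respective tracers at plateau. F is respective tracer infusion rate into a venous side". E "is expressed as tracer-to-tracee ratio (TTR) for calculation of PB".
- PS = 25 × (Ra,Phe − hydroxylation). There is no separate term for ingested phenylalanine.
- PB = 25 × (Ra,Phe − F_Phe) − PRO_MEAL. PRO_MEAL is 85% of the EAA ingested, in grams of EAA. The stated reason is that "contribution from exogenous EAA and tracers infused will be subtracted from total Ra".
- NB = PS − PB.

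Section B5.3 (Experimental Design and Figure 6) says that the drink's phenylalanine is enriched with the infused ring-2H5 tracer "to 4% to limit potential disturbances in isotopic steady-state". No equation adds this oral tracer to F.

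Hypothesis 3 in section B4 expects net balance to be more positive at the higher dose "due to a greater increase in whole-body protein synthesis". Section B5.1 names muscle protein synthesis and whole-body protein balance as the primary outcomes. Section B5.8.2 tests the effect of dose on whole-body turnover.

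**The concern.** F/E shows an unlabelled meal because the meal dilutes plasma enrichment. A drink labelled close to plasma enrichment hardly dilutes it, which is why it was labelled. Holding E steady and reading the meal from a fall in E are incompatible unless the oral tracer is counted as tracer input.

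The plan nonetheless treats F/E as a total that contains the meal. PS then lacks the ingested phenylalanine that F/E did not detect, and PB subtracts a meal contribution that Ra already omits in part or in full. The high dose is three times the low dose, so the error in PS and in PB does not cancel in the within-person comparison.

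Hypothesis 3 is at stake. It attributes the gain in balance to synthesis, while the background in section B2 sets out reduced breakdown as another route to a gain. The equations shift the apparent effect from the first to the second.

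**Working it through.** **Inputs from the documents.** Doses 0.10 and 0.30 g/kg; 0.63 g phenylalanine per 10 g of mixture (6.3%); drink enrichment e = 4%; absorbed fraction 0.85; 3-h window after the drink; factor 25 from phenylalanine to protein.

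**Assumptions (not in the documents).** Body mass 80 kg; endogenous Ra, R, of 0.6 to 1.0 µmol/kg/min; plasma plateau before the drink, F/R, of 4% to 10%; absorption complete within 3 h; dose has no effect on R or on hydroxylation. Molar mass of phenylalanine is 165.19 g/mol. The plan gives neither the tracer infusion rate nor the expected plateau.

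**Step 1: absorbed phenylalanine rate, X.**
X = dose × 0.063 × 0.85 / 165.19 × 10⁶ / 180 = 0.180 (low) and 0.540 (high) µmol/kg/min.
Conversion to protein: 25 × 165.19 × 10⁻⁶ × 180 × 80 = 59.47 g/3 h per µmol/kg/min.
True PS contrast under the assumptions: (0.540 − 0.180) × 59.47 = 21.4 g/3 h. True PB contrast: 0.

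**Step 2: what F/E returns.**
E = (F + eX)/(R + X), so F/E = F(R + X)/(F + eX).
At a 4% plateau F = 0.04R, E stays at 4% and F/E = R whatever the dose: all of X is missed.
At a 10% plateau with R = 0.8 (F = 0.08):
- low: E = 0.0872/0.9801 = 8.90%, F/E = 0.899, against a true total of 0.980;
- high: E = 0.1016/1.3403 = 7.58%, F/E = 1.055, against a true total of 1.340.

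So 45% (low) and 53% (high) of X are missed.

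**Step 3: contrasts as written.**
PS contrast = 59.47 × difference in F/E. PB contrast = PS contrast − difference in PRO_MEAL, where that difference is 0.85 × 80 × (0.30 − 0.10) = 13.6 g. For the cell above: PS 9.3 g, PB 9.3 − 13.6 = −4.3 g. Over R = 0.6 to 1.0:

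| Plateau | PS contrast returned (true 21.4 g/3 h) | PB contrast returned (true 0) |
|---|---|---|
| 4% | 0 | −13.6 |
| 6% | 3.7 to 4.7 | −8.9 to −9.9 |
| 8% | 6.4 to 7.7 | −5.9 to −7.2 |
| 10% | 8.4 to 9.9 | −3.7 to −5.2 |

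The PB column also contains a unit mismatch: PRO_MEAL is in grams of EAA, while Ra is scaled as 25 × phenylalanine. Per 10 g of mixture these are 8.5 g and 0.63 × 0.85 × 25 = 13.4 g.

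**Step 4: net balance.**
NB = 25(Ra − hydroxylation) − 25(Ra − F_Phe) + PRO_MEAL = 25(F_Phe − hydroxylation) + PRO_MEAL.
Ra,Phe drops out. The NB contrast is 13.6 g in every cell, with or without oral tracer in F.

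**Step 5: effect of the corrections.**
Replacing F by F + eX gives Ra = R + X at any plateau.
- F corrected, PRO_MEAL kept: PS contrast 21.4, PB contrast 21.4 − 13.6 = +7.8, NB contrast 13.6 g.
- F corrected and the PB subtraction changed to 25 × absorbed phenylalanine: PS 21.4, PB 0, NB 21.4 g.

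**The case against.** Four points can be made for the plan.

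- **The labelled drink and the spline fit already deal with the bolus.** The label keeps E steady, and that is what hides the meal from F/E. The spline changes how E is read, not what F contains. This does not rescue the formula.
- **The primary outcomes are not biased by this fault.** This stands. Ra,Phe cancels in NB, and muscle FSR uses bound and precursor enrichments, not F. A reader might infer from a dose-dependent error in both PS and PB that the balance comparison is biased too; the plan's own equations show otherwise.
- **The plateau is unknown.** This also stands. A reader might take the 4% label to mean that all ingested phenylalanine is lost, in exact proportion to dose. That needs a 4% plateau, which the stated purpose of the label suggests but the documents do not give. At 10% roughly half is lost and the PS contrast stays positive, so rejection of hypothesis 3 does not follow automatically. PS is still understated for any labelled drink. PB stays understated until the plateau exceeds about 13% (low dose) or 16% (high dose), taking R = 0.75 µmol/kg/min (45 µmol/kg/h).
- **One could keep F/E as endogenous Ra, drop PRO_MEAL and add absorbed phenylalanine to PS.** That is right only at a matched 4% plateau. At 10% it gives a PS contrast of 29.9 to 31.3 g and a spurious PB rise of 8.4 to 9.9 g, larger than the PB error it replaces.

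**Conclusion.** The concern holds for the separate whole-body synthesis and breakdown results after the drink, and so for the attribution to synthesis in hypothesis 3. As written, the equations understate PS, more at the higher dose, and across plateaus of 4% to 10% they create a fall in PB that did not occur. Under the stated assumptions 54% to 100% of the true 21.4 g PS contrast is lost (11.5/21.4 at a 10% plateau with R = 1.0; all of it at 4%). The direction of the PS error follows from the plan's equations whenever the drink is labelled; its size rests on the assumed plateau, endogenous Ra, body mass and absorption.

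The fault does not bias net balance or muscle FSR, and hypotheses 1, 2 and 4 are untouched by it. The unit of PRO_MEAL is a different matter: it does enter net balance, and it has to be settled in its own right. The equations should be corrected before synthesis and breakdown are analysed.

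**What to change.** 1. **Count the oral tracer.** For the 3-h window after the drink, compute total Ra as (F_iv + absorbed oral tracer)/E, integrated over the spline fit, and use it in both PS and PB. Oral tracer = 4% × phenylalanine in the drink × 0.85. State how its entry is spread over the 3 h. Keep F/E for the period before the drink.
2. **As a separate, declared correction,** make the PB subtraction 25 × absorbed phenylalanine instead of grams of EAA. Without it, step 1 leaves a spurious PB contrast of about +7.8 g. With it, the net balance contrast moves from 13.6 to 21.4 g under the assumptions above, so the sponsor should state that a primary outcome changes.
3. **Report** the tracer infusion rate and the observed plateau before the drink, and add a sensitivity analysis on the 85% absorption.

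The cost is rewording the equations and running one sensitivity analysis. No new samples or assays are needed.

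### The breakdown equation credits the drink in grams of EAA instead of phenylalanine × 25; on a common time basis this makes the net-balance dose contrast 0.098–0.123 g/kg too small on the plan's own scale (up to 0.152 without arginine)

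*Combined protocol and SAP*

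**What the plan says.** All of this is in B5.4, under the whole-body turnover and muscle synthesis calculations, except the drink composition, which is in B5.3, Experimental Design.

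- The basis of the method is phenylalanine alone. Turnover comes from "dividing kinetic values of a single essential amino acid (i.e., phenylalanine), which cannot be synthesized in the body, by its fractional contribution to protein". The factor of 25 rests on the "assumption that contribution of phenylalanine to protein is 4"%.
- The prose on breakdown says that the "contribution from exogenous EAA and tracers infused will be subtracted from total Ra".
- The printed equation is "PB = [(R_{a|Phe} - F_{Phe}) \times 25 - PRO_{MEAL"}]. The infused tracer is removed inside the bracket that is multiplied by 25; the drink is removed outside it.
- The drink term is defined in grams: it "is the amount of exogenous EAA (g) that appeared in the circulation, which was calculated as total amount of EAA provided (if any").
- How much of the drink counts as taken up is fixed in advance, "based on the assumption that 85% of the EAA ingested was absorbed".
- Net balance is synthesis minus breakdown. Synthesis is 25 times the difference between phenylalanine Ra and phenylalanine hydroxylation.
- The drink provides "0.63 g phenylalanine" in a list headed "EAA content per 10 g of the mixture", which also includes 0.81 g arginine.

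B5.1 names whole-body protein balance as a primary outcome, with muscle protein synthesis. Hypothesis 2 in B4 predicts a greater balance at 0.30 than at 0.10 g/kg.

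**The concern.** Every term in the balance except one is phenylalanine multiplied by 25. The exception is the drink, which is entered as grams of amino acids. The two scales agree only for a source that is 4% phenylalanine, and this free-form mixture is not.

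The mismatch does not cancel in the crossover, because the drink term is the one that differs by design between the two trials. At stake is the dose contrast in a primary outcome. There is also a practical problem for the analyst. The prose removes the exogenous contribution from Ra, and only phenylalanine can be taken from a phenylalanine Ra. The equation removes grams of EAA after conversion. The two instructions give different answers.

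**Working it through.** **The plan's own factor.** 100/4 = 25, as stated.

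**Net balance from the printed equations** (Ra = phenylalanine Ra, F = infused phenylalanine tracer, H = hydroxylation):

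NB = 25(Ra − H) − [25(Ra − F) − PRO_MEAL] = 25(F − H) + PRO_MEAL

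Ra cancels, so any error in PRO_MEAL enters NB one for one. If the drink is instead removed as absorbed phenylalanine inside the bracket, NB = 25(F − H) + 25 × absorbed drink phenylalanine. Only the drink term changes.

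**Inputs.**
- Doses of 0.10 and 0.30 g/kg (B4), a difference of 0.20 g/kg.
- Absorption 0.85 (B5.4), so the difference in absorbed dose is 0.20 × 0.85 = 0.170 g/kg.
- Drink composition (B5.3): the listed items sum to 0.15 + 3.66 + 0.94 + 1.65 + 0.3 + 0.63 + 0.89 + 0.1 + 0.006 + 0.81 = 9.136 g per 10 g, or 8.326 g without arginine.

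**Value of one absorbed gram of mixture.** 25 × 0.063 = 1.575 g on the plan's scale, credited as 1 g.

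**Gap in the high-minus-low contrast** over the post-drink period = 0.170 × (25p − c), where p is the phenylalanine share of the dose and c the share of the dose credited through PRO_MEAL. The documents do not say whether g/kg means mixture or listed amino acids, so each reading is shown.

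| g/kg means | PRO_MEAL credits | p | c | Printed, 0.17c | Consistent, 0.17 × 25p | Gap (g/kg) | Printed ÷ consistent |
|---|---|---|---|---|---|---|---|
| mixture | whole mixture | 0.0630 | 1 | 0.170 | 0.268 | 0.098 | 0.63 |
| mixture | listed items, with arginine | 0.0630 | 0.9136 | 0.155 | 0.268 | 0.112 | 0.58 |
| listed items, with arginine | the same | 0.0690 | 1 | 0.170 | 0.293 | 0.123 | 0.58 |
| mixture | nine EAA, no arginine | 0.0630 | 0.8326 | 0.142 | 0.268 | 0.126 | 0.53 |
| nine EAA, no arginine | the same | 0.0757 | 1 | 0.170 | 0.322 | 0.152 | 0.53 |

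With arginine counted as listed, the gap is 0.098–0.123 g/kg. Without it, the gap reaches 0.152 g/kg. At an assumed 80 kg these are 7.8–9.8 g and up to 12.1 g.

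**Sensitivity to other readings.** Dropping the 85% on both sides gives 0.115–0.178. Applying it to the phenylalanine side only gives 0.068–0.122. Counting phenylalanine as 0.96 or 1.04 of the listed amount, because of the 4% label, gives 0.087–0.164. The sign is the same in all of them.

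**Related point, direction only.** The drink phenylalanine carries the same label as the infusion, but F is defined as the venous infusion alone. After the drink, F/E therefore under-registers Ra, more so at the higher dose, and lowers PS and PB equally. NB is untouched because Ra cancels. The size needs Ra and enrichment values that the documents do not give.

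**The case against.** Several objections limit the point.

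*The prose may already give the right method.* It can be read as a loose description of the equation below it, since it does not say whether the subtraction comes before or after the × 25. So this is not an explicit contradiction. But B5.4 says that the printed equations are the ones to be used, and the gram definition of PRO_MEAL is explicit. The passages still need to be reconciled.

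*The direction depends on the time basis.* PRO_MEAL is an amount, Ra and F are rates, and no window is given for the conversion. A reader might infer that a period total will be set against hourly rates, which would make the contrast too large. The documents give no units for whole-body Ra or F and nothing says this will happen. What stands is that the stated direction holds only on a common time basis.

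*The yardstick is the plan's own convention.* This objection stands. The gap measures internal inconsistency against the phenylalanine × 25 scale, not bias against true protein balance.

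*The contrast might change sign.* With F equal in both trials, the printed contrast would reach zero if 53–63% of the extra absorbed phenylalanine were hydroxylated (the last column of the table). No hydroxylation value is given, so the documents do not support a claim of reversal.

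*The split between synthesis and breakdown.* The drink credit raises PB at the high dose relative to the low dose, while the uncounted drink label lowers it. A reader might infer from the label effect alone that the result tilts towards breakdown, but the net effect on PB is not determined.

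**Conclusion.** The printed breakdown equation is not on the scale that the plan sets for itself, and the error goes unchanged into a primary outcome. With all terms on one time basis and 85% absorption on both sides, the high-minus-low contrast in net balance over the post-drink period is 0.098–0.123 g/kg too small on the phenylalanine × 25 scale when arginine is counted, and up to 0.152 g/kg too small when it is not. It is proportional to the randomised dose and works against hypothesis 2.

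The documents do not show how much this matters against the expected effect. B5.8.1 claims more than 95% power for balance but gives no effect size or SD. A reader might infer that this power is lost; that can be neither shown nor excluded. Muscle FSR, the other primary outcome and the basis of the sample size, is not affected.

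**What to change.** Make these changes together, before analysis:

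1. Replace PRO_MEAL by absorbed drink phenylalanine (0.85 × phenylalanine ingested), as a rate over the 3-h post-drink period, and subtract it from Ra inside the × 25 bracket.
2. State whether the g/kg dose means mixture or listed amino acids, whether arginine counts, and whether the 0.63 g includes the added label.
3. Use one enrichment convention throughout. Either take total Ra and subtract both infused and drink tracer along with the unlabelled drink phenylalanine; or take tracee-only Ra from TTR, subtract only the unlabelled drink phenylalanine, and do not subtract F_Phe again. Moving to the second option shifts the level of NB by 25F in both trials, so changing PRO_MEAL alone would correct the dose contrast but not the level.
4. Under either convention, count the absorbed drink label as tracer input when computing post-drink Ra.
5. The drink term reveals the dose. Have the code-holder named in B5.1 apply it and return the results under coded labels.
6. Report NB over a range of absorption fractions.

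The cost is rewording, minor recoding and a small extra task for the code-holder. No new data are needed. The corrected result still depends on the assumed absorption and on the chosen window, which is why the sensitivity range belongs in the report.
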